APPENDIX C: Management Algorithms

These general guidelines constitute guidance to the Investigator and may be supplemented by discussions with the IND Sponsor. The guidance applies to all immuno-oncology (I-O) agents and regimens.

A general principle is that differential diagnoses should be diligently evaluated according to standard medical practice. Non-inflammatory etiologies should be considered and appropriately treated.

[figure not shown]
Corticosteroids are a primary therapy for immuno-oncology drug-related adverse events. The oral equivalent of the recommended IV doses may be considered for ambulatory subjects with low-grade toxicity. The lower bioavailability of oral corticosteroids should be taken into account when switching to the equivalent dose of oral corticosteroids.

Consultation with a medical or surgical specialist, especially prior to an invasive diagnostic or therapeutic procedure, is recommended.

The frequency and severity of the related adverse events covered by these algorithms will depend on the immuno-oncology agent or regimen being used.

Endocrinopathy Management Algorithm

[figure not shown]
Rule out non-inflammatory causes. If non-inflammatory cause, treat accordingly and continue I-O therapy. Consider visual field testing, endocrinology consultation, and imaging.

Patients on IV steroids may be switched to an equivalent dose of oral corticosteroids (e.g. prednisone) at start of tapering or earlier, once sustained clinical improvement is observed. Lower bioavailability of oral corticosteroids should be taken into account when switching to the equivalent dose of oral corticosteroids.

GI Adverse Event Management Algorithm

[figure not shown]
Rule out non-inflammatory causes. If non-inflammatory cause is identified, treat accordingly and continue I-O therapy. Opiates/narcotics may mask symptoms of perforation. Infliximab should not be used in cases of perforation or sepsis.

Patients on IV steroids may be switched to an equivalent dose of oral corticosteroids (e.g. prednisone) at start of tapering or earlier, once sustained clinical improvement is observed. Lower bioavailability of oral corticosteroids should be taken into account when switching to the equivalent dose of oral corticosteroids.

Hepatic Adverse Event Management Algorithm

Rule out non-inflammatory causes. If non-inflammatory cause, treat accordingly and continue I-O therapy. Consider imaging for obstruction.

[figure not shown]
Patients on IV steroids may be switched to an equivalent dose of oral corticosteroids (e.g. prednisone) at start of tapering or earlier, once sustained clinical improvement is observed. Lower bioavailability of oral corticosteroids should be taken into account when switching to the equivalent dose of oral corticosteroids.

*I-O therapy may be delayed rather than discontinued if AST/ALT ≤ 8 x ULN or T.bili ≤ 5 x ULN.

**The recommended starting dose for grade 4 hepatitis is 2 mg/kg/day methylprednisolone IV.

Neurological Adverse Event Management Algorithm

[figure not shown]
Rule out non-inflammatory causes. If non-inflammatory cause, treat accordingly and continue I-O therapy.

Patients on IV steroids may be switched to an equivalent dose of oral corticosteroids (e.g. prednisone) at start of tapering or earlier, once sustained clinical improvement is observed. Lower bioavailability of oral corticosteroids should be taken into account when switching to the equivalent dose of oral corticosteroids.

Pulmonary Adverse Event Management Algorithm

[figure not shown]
Rule out non-inflammatory causes. If non-inflammatory cause, treat accordingly and continue I-O therapy. Evaluate with imaging and pulmonary consultation.

Patients on IV steroids may be switched to an equivalent dose of oral corticosteroids (e.g. prednisone) at start of tapering or earlier, once sustained clinical improvement is observed. Lower bioavailability of oral corticosteroids should be taken into account when switching to the equivalent dose of oral corticosteroids.

Renal Adverse Event Management Algorithm

[figure not shown]
Rule out non-inflammatory causes. If non-inflammatory cause, treat accordingly and continue I-O therapy

Patients on IV steroids may be switched to an equivalent dose of oral corticosteroids (e.g. prednisone) at start of tapering or earlier, once sustained clinical improvement is observed. Lower bioavailability of oral corticosteroids should be taken into account when switching to the equivalent dose of oral corticosteroids.

Skin Adverse Event Management Algorithm

Rule out non-inflammatory causes. If non-inflammatory cause, treat accordingly and continue I-O therapy.

Patients on IV steroids may be switched to an equivalent dose of oral corticosteroids (e.g. prednisone) at start of tapering or earlier, once sustained clinical improvement is observed. Lower bioavailability of oral corticosteroids should be taken into account when switching to the equivalent dose of oral corticosteroids.

*Refer to NCI CTCAE v4 for term-specific grading criteria.

^If SJS/TEN is suspected, withhold I-O therapy and refer patient for specialized care for assessment and treatment. If SJS or TEN is diagnosed, permanently discontinue I-O therapy.

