Drug-related AEs	Grade (CTCAE v5.0) or measurement	Action taken to study drugs	Retreatment Dose Level	AE management	Monitor and follow-up
	Grade ≥ 3	Withhold	Decrease by one dose level at the PI's discretion	
 • Treatment with transfusion or growth factors allowed at PI's discretion 	
Other non-hematological toxicities	Grade 3	Withhold	1 st : no dose change 2 nd -3 rd : decrease by one dose level 4 th : discontinue		
	Grade 4 or any toxicity requiring delay for >21 days	Permanently discontinue	N/A		

 1. Persistent occurrence is defined as repeated post-infusion blood glucose measurements taken at different times during the cycle despite optimal glucose-lowering therapy in consultation with endocrinologist 2. Infusion may proceed/resume on scheduled day if BP recovers to <150/90 mmHg for 2 consecutive measurements and symptoms (if present) resolve. 3. Despite maximum supportive therapy 4. Thrombocytopenia, neutropenia, febrile neutropenia, anemia, INR or PTT with bleeding 
General instructions:
 
 • For situations where drug is withheld due to a copanlisib-related AE, treatment can be resumed after AE has been reduced to Grade 1 or 0 unless otherwise indicated. Treatment should be permanently discontinued if AE does not resolve within 12 weeks of last dose. • If patient is already on lowest dose level and meets criteria for further decrease, study drug will be discontinued permanently. • Dose re-escalation may be allowed at the PI's discretion after patient has fully recovered from the toxicity and in the absence of any other adverse events that require dose-reduction, with the exception of non-infectious pneumonitis. • Abbreviations: SGLT2 = Sodium/Glucose co-transporter 2; DPP4 = Dipeptidyl peptidase 4; PJP= pneumocystis jiroveci pneumonia 					

In order to standardize the management of AEs for all subjects, treatment management algorithms are included in **Appendix C**. Additional AE treatment management algorithms included in the nivolumab IB might be considered for individual cases.

Subjects who require a delay in study treatment should be re-evaluated weekly or more frequently if clinically indicated and resume dosing when re-treatment criteria are met.

Subjects may resume treatment with study drug when the nivolumab-related AE(s) resolve to grade ≤ 1 or baseline value, with the following exceptions:

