4.4.2 Toxicity-Related Treatment Discontinuation

In addition to the discontinuation criteria listed in **Table 4** above, permanent discontinuation of study treatment should be considered for any severe or life-threatening treatment-related AEs, including, but not limited to, any of the following (the IND Sponsor and BMS must be notified in the event of these AEs):

- Any grade 2 treatment-related uveitis, eye pain, or blurred vision that does not respond to topical therapy and does not improve to Grade 1 severity within 2 weeks of starting therapy OR requires systemic treatment
- Any grade 3 non-skin, drug-related AE lasting > 7 days, with the following exceptions:
 - Grade 3 treatment-related uveitis, pneumonitis, bronchospasm, diarrhea, colitis, myocarditis, neurologic toxicity, hypersensitivity reaction, or infusion reaction of any duration requires discontinuation
 - Grade 3 treatment-related endocrinopathies adequately controlled with only physiologic hormone replacement do not require discontinuation. Treatment should be discontinued for grade 3 adrenal insufficiency.
 - Grade 3 treatment-related laboratory abnormalities do not require treatment discontinuation except:
 - Grade 3 treatment-related thrombocytopenia > 7 days **or** that is associated with bleeding requires discontinuation

- Any treatment-related liver function test (LFT) abnormality that meets the following criteria require discontinuation:
 - Total bilirubin $> 5 \times \text{ULN}$
 - Concurrent AST or ALT $> 3 \times \text{ULN}$ **and** total bilirubin $> 2 \times \text{ULN}$
- Any grade 4 treatment-related AE or laboratory abnormality, except for the following events which do not require discontinuation:
 - Grade 4 amylase or lipase abnormalities that are not associated with symptoms or clinical manifestations, or radiographic signs of pancreatitis.
 - Isolated grade 4 electrolyte imbalances/abnormalities that are not associated with clinical sequelae and are corrected with supplementation/appropriate management within 72 hours of their onset.
 - Grade 4 lymphopenia and leukopenia.
 - Grade 4 treatment-related endocrinopathy adverse events, such as ACTH deficiency, hyper- or hypothyroidism, or glucose intolerance, which resolve or are adequately controlled with physiologic hormone replacement (corticosteroids, thyroid hormones) or glucose-controlling agents, respectively, may not require discontinuation after discussion with and approval from the IND Sponsor.

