4.5 Duration of Therapy and Criteria for Removal from Study Treatment

In the absence of treatment delays due to adverse event(s), treatment may continue indefinitely until one of the following criteria applies. The reason for study treatment removal and the date the patient was removed must be documented in the Case Report Form.

A participant must be discontinued from study treatment but continue to be monitored in the study follow-up for any of the following reasons:

- The participant or participant's legally acceptable representative requests to discontinue study treatment
- Confirmed radiographic disease progression outlined in **Section 9** and **Appendix E**
 - As immunotherapy has been shown to cause pseudo-progression, patients are eligible to remain on study after progression if they are clinically stable, if they desire and their treating physician agrees it is in the interest of the patient. If subsequent imaging confirms progression, the patient's date of progression will be the date of first progression
- Clinical progression or deterioration

- Progression or recurrence of any malignancy, or any occurrence of another malignancy that requires active treatment
- Unacceptable adverse experiences as described in **Section 4.4.2** Exceptions must be approved by the IND Sponsor.
- The participant has a medical condition or personal circumstance which, in the opinion of the investigator and/or sponsor, placed the participant at unnecessary risk from continued administration of study treatment.
- Investigator's decision to withdraw the subject
- The participant has a confirmed positive serum pregnancy test
- Noncompliance with study treatment or procedure requirements

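### Appendix C's hepatic footnote, as legible, allows nivolumab to be delayed in a range of combined AST/ALT and bilirubin elevation where Sections 4.4.2 and 4.5 require discontinuation unless the IND Sponsor approves an exception (minor)

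*Combined protocol and SAP*

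**What the plan says.** Three places bear on treatment-related liver abnormalities.

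- **Section 4.4.2** opens by saying that permanent discontinuation should be considered for severe events, and adds that "the IND Sponsor and BMS must be notified in the event of these AEs". Its liver item is firmer: "Any treatment-related liver function test (LFT) abnormality that meets the following criteria require discontinuation". The two criteria are total bilirubin above 5x ULN, and AST or ALT above 3x ULN concurrent with total bilirubin above 2x ULN.
- **Section 4.5** is mandatory: "A participant must be discontinued from study treatment but continue to be monitored in the study follow-up for any of the following reasons". The reasons listed include unacceptable adverse experiences as described in Section 4.4.2, with the qualifier "Exceptions must be approved by the IND Sponsor".
- **Appendix C**, in an asterisked footnote to the hepatic algorithm, says "I-O therapy may be delayed rather than discontinued if AST/ALT ≤ 8 x ULN or T.bili ≤ 5 x ULN". The footnote does not mention Section 4.4.2, Section 4.5 or any approval.

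Two sentences describe the standing of Appendix C. Its preamble says "These general guidelines constitute guidance to the Investigator and may be supplemented by discussions with the IND Sponsor". Section 4.4.1 introduces it with "In order to standardize the management of AEs for all subjects, treatment management algorithms are included in" Appendix C.

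**The concern.** An investigator who sees a combined transaminase and bilirubin rise finds one place in the protocol that calls for stopping treatment and another that allows nivolumab to be delayed. Under the footnote, the next step would be the general resumption rule in Section 4.4.1: "Subjects may resume treatment with study drug when the nivolumab-related AE(s) resolve to grade" 1 or lower, or baseline.

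At stake is one safeguard. A site relying on the footnote could resume nivolumab without the IND Sponsor approval that Section 4.5 demands for an exception. Because the study is multi-center, two sites could also manage the same liver signal differently. DLT counting, SAE reporting and the efficacy endpoints are not affected.

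**Working it through.** No sample size, power or error rate is involved. The check compares two sets of inequalities. Let *a* be AST or ALT and *b* be total bilirubin, both as multiples of ULN.

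**Inputs**

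- Discontinue (Section 4.4.2 liver item, made mandatory by Section 4.5): *b* > 5, or (*a* > 3 and *b* > 2).
- Delay allowed (Appendix C hepatic footnote): *a* ≤ 8 or *b* ≤ 5.
- Dosing hold (Section 4.4.1): *a* > 3 or *b* > 1.5 (*b* > 2.0 in Gilbert's syndrome).
- DILI definition (Section 5.1.2): *a* ≥ 3 and *b* ≥ 2, with alkaline phosphatase below 2x ULN.

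**Step 1: the overlap.** Take the region 3 < *a* ≤ 8 and 2 < *b* ≤ 5.

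- Every point has *a* > 3 and *b* > 2, so the concurrent criterion in Section 4.4.2 is met.
- Every point has *a* ≤ 8 and also *b* ≤ 5, so the footnote is satisfied whether its connector is read as written or as a loosely worded 'and'.

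Example: *a* = 5, *b* = 3. Discontinue, because 5 > 3 and 3 > 2. Delay allowed, because 5 ≤ 8 and 3 ≤ 5. Both rules apply.

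**Step 2: which other provisions apply in that region.**

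| Provision | Applies here? | Is it IND Sponsor approval? |
|---|---|---|
| 4.4.1 dosing hold | Always, since *a* > 3 | No. It delays dosing until *a* ≤ 3 and *b* ≤ 1.5 (≤ 2.0 in Gilbert's) |
| 4.4.2 notification of IND Sponsor and BMS | Yes | No. It informs only |
| 5.1.2 and 5.6.1, DILI handled as an SAE and reported within 24 hours | If alkaline phosphatase is below 2x ULN | No. It reports only |
| 4.4.1, PI approves retreatment | Only if the start of a cycle slips by more than 1 week | No, unless the PI is also the IND Sponsor |
| 4.4.5, steroids finished at least 14 days before resuming | If steroids were used | No. It is a washout |

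**Step 3: when PI approval would be triggered.** On the nominal 28-day cycle the next Day 1 falls on day 29, and the trigger is a slip of more than 7 days. Recovery must therefore take longer than:

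- event found on Day 1: 7 days;
- event found on Day 8: (29 − 8) + 7 = 28 days;
- event found on Day 15: (29 − 15) + 7 = 21 days.

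A quicker recovery would not bring in PI approval. If the event is attributed to copanlisib, Table 4 separately requires permanent discontinuation once a non-hematological toxicity forces a delay of more than 21 days.

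**The case against.** The strongest reply is that guidance which permits something cannot override a rule that forbids it. Appendix C calls itself guidance and says that it covers all immuno-oncology agents and regimens, so it is generic. Sections 4.4.2 and 4.5 are specific to this trial and use mandatory words. A site that discontinues complies with everything; a site that leans on the footnote departs from Section 4.5. This largely stands, and it is why the point is minor. It does not dispose of the matter. No legible sentence gives the order of precedence, Section 4.4.1 brings the algorithms in as the standard for all subjects, and the preamble makes discussion with the IND Sponsor optional.

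Second, the footnote qualifies a box in a figure that is not visible in the available text. That box might be limited to isolated transaminase elevation, or might itself point to the discontinuation rule. This also stands, so the point is confined to the legible wording.

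Third, Section 4.4.5 makes continuation on study treatment depend on agreement of the investigator, the Sponsor and the participant. That sentence follows the list of prohibited therapies and concerns patients who need one of them or other supportive care. Extending it to a liver event is arguable at best.

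Fourth, the opening of Section 4.4.2 only asks that discontinuation be considered. The liver item within it says discontinuation is required, and Section 4.5 says must, so the softer opening does not settle the question.

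A reader might infer three stronger things that the documents do not support:

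- *That the protocol permits dosing during combined liver injury.* It does not. The footnote speaks of delay, and Section 4.4.1 bars dosing until the values recover.
- *That the footnote's 'or' is a slip for 'and' and should be corrected.* Read literally, 'or' does widen the overlap: AST/ALT above 8x with bilirubin above 2x to 5x, and AST/ALT up to 8x with bilirubin above 5x, would also meet both rules. But changing the connector would also remove the delay option for isolated AST/ALT above 8x with low bilirubin, a pattern that the Section 4.4.2 liver criteria do not list. Whether that is intended cannot be judged without the figure.
- *That copanlisib may be continued or resumed on the strength of the footnote.* It addresses I-O therapy only, taken here to mean nivolumab.

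**Conclusion.** There is a minor inconsistency between two safety rules. It is claimed for treatment-related AST/ALT above 3x to 8x ULN with total bilirubin above 2x to 5x ULN, where the two rules overlap under either reading of the footnote's connector. Sections 4.4.2 and 4.5 probably prevail. The possible consequence is that nivolumab is resumed, after recovery, without the IND Sponsor's approval of an exception.

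The conclusion assumes that the unseen algorithm box contains no limit that removes the overlap. Its practical weight also depends on who the IND Sponsor is: names are removed, so it cannot be checked whether the PI holds both roles, and if so PI approval would close much of the gap whenever it is triggered. The documents give no hepatic event rate, so no count of affected patients can be offered.

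**What to change.** Keep the footnote's two thresholds and its 'or' unchanged, and append: *except where Section 4.4.2 requires discontinuation (total bilirubin >5x ULN, or concurrent AST/ALT >3x ULN with total bilirubin >2x ULN), unless the IND Sponsor approves an exception per Section 4.5*.

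Because the clause names both liver criteria of Section 4.4.2, it removes the conflict by construction under either reading of the connector. It keeps sponsor-approved exceptions available and leaves isolated transaminase elevation as the footnote now has it.

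The cost is one reworded footnote, which can go into the next amendment. AST, ALT and total bilirubin are already in the chemistry panel on every treatment day in the Section 8 calendars, so no tests or visits are added.

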APPENDIX D: Average Glycemic Index of Common Foods

The average Glycemic Index of common foods derived from multiple studies by different laboratories

Foods are categorized as having a low-glycemic index if the glucose reference index is ≤ 55 . High-Glycemic Index foods have a glucose reference index >55 . The summary table below contains glucose reference for common foods.

High-carbohydrate foods		Breakfast cereals		Fruit and fruit products		Vegetables	
White wheat bread*	75 ± 2]	Cornflakes	81 ± 6	Apple, raw†	36 ± 2	Potato, boiled	78 ± 4
Whole wheat/whole meal bread	74 ± 2	Wheat flake biscuits	69 ± 2	Orange, raw†	43 ± 3	Potato, instant mash	87 ± 3
Specialty grain bread	53 ± 2	Porridge, rolled oats	55 ± 2	Banana, raw†	51 ± 3	Potato, french fries	63 ± 5
Unleavened wheat bread	70 ± 5	Instant oat porridge	79 ± 3	Pineapple, raw	59 ± 8	Carrots, boiled	39 ± 4
Wheat roti	62 ± 3	Rice porridge/congee	78 ± 9	Mango, raw†	51 ± 5	Sweet potato, boiled	63 ± 6
Chapati	52 ± 4	Millet porridge	67 ± 5	Watermelon, raw	76 ± 4	Pumpkin, boiled	64 ± 7
Corn tortilla	46 ± 4	Muesli	57 ± 2	Dates, raw	42 ± 4	Plantain/green banana	55 ± 6
White rice, boiled*	73 ± 4			Peaches, canned†	43 ± 5	Taro, boiled	53 ± 2
Brown rice, boiled	68 ± 4			Strawberry jam/jelly	49 ± 3	Vegetable soup	48 ± 5
Barley	28 ± 2			Apple juice	41 ± 2		
Sweet corn	52 ± 5			Orange juice	50 ± 2		
Spaghetti, white	49 ± 2						
Spaghetti, whole meal	48 ± 5						
Rice noodles†	53 ± 7						
Udon noodles	55 ± 7						
Couscous†	65 ± 4						
Dairy products and alternatives		Legumes		Snack products		Sugars	
Milk, full fat	39 ± 3	Chickpeas	28 ± 9	Chocolate	40 ± 3	Fructose	15 ± 4
Milk, skim	37 ± 4	Kidney beans	24 ± 4	Popcorn	65 ± 5	Sucrose	65 ± 4
Ice cream	51 ± 3	Lentils	32 ± 5	Potato crisps	56 ± 3	Glucose	103 ± 3
Yogurt, fruit	41 ± 2	Soya beans	16 ± 1	Soft drink/soda	59 ± 3	Honey	61 ± 3
Soy milk	34 ± 4			Rice crackers/crisps	87 ± 2		
Rice milk	86 ± 7						

Data are means ± SEM. *Low-GI varieties were also identified. †Average of all available data.

APPENDIX E: Response Evaluation Criteria in Solid Tumors (RECIST) 1.1 Criteria for Evaluating Response in Solid Tumors

RECIST version 1.1 will be used in this study for assessment of tumor response. While either CT or MRI may be used, as per RECIST 1.1, CT is the preferred imaging technique in this study.

Disease Parameters

Measurable disease: Measurable lesions are defined as those that can be accurately measured in at least one dimension (longest diameter to be recorded) as ≥ 20 mm by chest x-ray, as ≥ 10 mm with CT scan, or ≥ 10 mm with calipers by clinical exam. All tumor measurements must be recorded in millimeters (or decimal fractions of centimeters).

Note: Tumor lesions that are situated in a previously irradiated area might or might not be considered measurable unless there is evidence of progression in the irradiated site. Malignant lymph nodes. To be considered pathologically enlarged and measurable, a lymph node must be ≥ 15 mm in short axis when assessed by CT scan (CT scan slice thickness recommended to be no greater than 5 mm). At baseline and in follow-up, only the short axis will be measured and followed.

Non-measurable disease: All other lesions (or sites of disease), including small lesions (longest diameter < 10 mm or pathological lymph nodes with ≥ 10 to < 15 mm short axis), are considered non-measurable disease. Bone lesions, leptomeningeal disease, ascites, pleural/pericardial effusions, lymphangitis cutis/pulmonitis, inflammatory breast disease, and abdominal masses (not followed by CT or MRI), are considered as non-measurable.

Note: Cystic lesions that meet the criteria for radiographically defined simple cysts should not be considered as malignant lesions (neither measurable nor non-measurable) since they are, by definition, simple cysts.

‘Cystic lesions’ thought to represent cystic metastases can be considered as measurable lesions, if they meet the definition of measurability described above. However, if non-cystic lesions are present in the same subject, these are preferred for selection as target lesions.

Target lesions: All measurable lesions up to a maximum of 2 lesions per organ and 5 lesions in total, representative of all involved organs, should be identified as **target lesions** and recorded and measured at baseline. Target lesions should be selected on the basis of their size (lesions with the longest diameter), be representative of all involved organs, but in addition should be those that lend themselves to reproducible repeated measurements. It may be the case that, on occasion, the largest lesion does not lend itself to reproducible measurement in which circumstance the next largest lesion which can be measured reproducibly should be selected. A sum of the diameters (longest for non-nodal lesions, short axis for nodal lesions) for all target lesions will be calculated and reported as the baseline sum diameters. If lymph nodes are to be included in the sum, then only the short axis is added into the sum. The baseline sum diameters will be used as reference to further characterize any objective tumor regression in the measurable dimension of the disease.

Non-target lesions: All other lesions (or sites of disease) including any measurable lesions over and above the 5 target lesions should be identified as **non-target lesions** and should also be

recorded at baseline. Measurements of these lesions are not required, but the presence, absence, or in rare cases unequivocal progression of each should be noted throughout follow-up.

Evaluation of Target Lesions

Complete Response (CR): Disappearance of all target lesions. Any pathological lymph nodes (whether target or non-target) must have reduction in short axis to <10 mm.

Partial Response (PR): At least a 30% decrease in the sum of the diameters of target lesions, taking as reference the baseline sum diameters.

Progressive Disease (PD): At least a 20% increase in the sum of the diameters of target lesions, taking as reference the smallest sum on study (this includes the baseline sum if that is the smallest on study). In addition to the relative increase of 20%, the sum must also demonstrate an absolute increase of at least 5 mm. (Note: the appearance of one or more new lesions is also considered progressions).

Stable Disease (SD): Neither sufficient shrinkage to qualify for PR nor sufficient increase to qualify for PD, taking as reference the smallest sum diameters while on study.

Evaluation of Non-Target Lesions

Complete Response (CR): Disappearance of all non-target lesions and normalization of tumor marker level. All lymph nodes must be non-pathological in size (<10 mm short axis).

Note: If tumor markers are initially above the upper normal limit, they must normalize for a subject to be considered in complete clinical response.

Non-CR/Non-PD: Persistence of one or more non-target lesion(s) and/or maintenance of tumor marker level above the normal limits.

Progressive Disease (PD): Appearance of one or more new lesions and/or *unequivocal progression* of existing non-target lesions. *Unequivocal progression* should not normally trump target lesion status. It must be representative of overall disease status change, not a single lesion increase.

Although a clear progression of “non-target” lesions only is exceptional, the opinion of the treating physician should prevail in such circumstances, and the progression status should be confirmed at a later time by the review panel (or Principal Investigator).

Evaluation of Best Overall Response

The best overall response is the best response recorded from the start of the treatment until disease progression/recurrence (taking as reference for progressive disease the smallest measurements recorded since the treatment started). The subject's best response assignment will depend on the achievement of both measurement and confirmation criteria.

For Subjects with Measurable Disease (i.e., Target Disease)

[figure not shown]
Target Lesions	Non-Target Lesions	New Lesions	Overall Response	Best Overall Response when Confirmation is Required*
CR	CR	No	CR	≥ 4 wks. Confirmation**
CR	Non-CR/Non-PD	No	PR	≥ 4 wks. Confirmation**
CR	Not evaluated	No	PR	
PR	Non-CR/Non-PD/not evaluated	No	PR	
SD	Non-CR/Non-PD/not evaluated	No	SD	Documented at least once ≥ 4 wks. from baseline**
PD	Any	Yes or No	PD	no prior SD, PR or CR
Any	PD***	Yes or No	PD	
Any	Any	Yes	PD	

* See RECIST 1.1 manuscript for further details on what is evidence of a new lesion.
 
** Only for non-randomized trials with response as primary endpoint.
 
*** In exceptional circumstances, unequivocal progression in non-target lesions may be accepted as disease progression.
 
Note: Subjects with a global deterioration of health status requiring discontinuation of treatment without objective evidence of disease progression at that time should be reported as “symptomatic deterioration.” Every effort should be made to document the objective progression even after discontinuation of treatment.
				

Reference

E.A. Eisenhauer, P. Therasse, J. Bogaerts, L.H. Schwartz, D. Sargent, R. Ford, J. Dancey, S. Arbuck, S. Gwyther, M. Mooney, L. Rubinstein, L. Shankar, L. Dodd, R. Kaplan, D. Lacombe, J. Verweij. New response evaluation criteria in solid tumours: Revised RECIST guideline (version 1.1). Eur J Cancer. 2009 Jan;45(2):228-47.

